## 7.2 Secondary Efficacy Analyses

## 7.2.1 HbA1c Change from Baseline over Time

The continuous secondary efficacy endpoint of HbA1c change from baseline by visit will be analyzed analogous to the primary endpoint using a 2 sample t-test. One analysis will be performed using the LOCF algorithm for all visits, and a separate analysis will be performed using OC algorithm. The OC algorithm analysis will exclude any post-rescue values.

Final – 22November2011 CONFIDENTIAL Page 21 of 30

The pattern of HbA1c over time and change from baseline over time will be evaluated both descriptively using summary statistics and graphically at each scheduled visit during the entire duration of the study, excluding post-rescue measurements. Descriptive summaries will also be provided including post-rescue measurements.

The analyses will be performed on the full analysis set and all data will be listed.

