During the run-in period, subjects will be instructed to determine daily self-monitored blood glucose (SMBG) after an overnight fast. The SMBG record will be reviewed by the investigator at each clinic visit. If the fasting blood glucose is > 216 mg/dL (12 mmol/L) in two consecutive days, the subject should contact the clinical staff. In addition, subjects will be instructed that they must contact the clinic within 24 h if SMBG is ≥ 270 mg/dL (15 mmol/L). If the fasting SMBG is ≥ 270 mg/dL (15 mmol/L) without explanations for the elevation, the investigator will review the SMBG record and determine if the subject should attempt to improve diet and exercise to maintain glycemic control or if the subject must discontinue from the study and resume diabetic medications. Subjects with symptomatic hyperglycemia or hypoglycemia should be withdrawn if the symptoms are severe.

During the 24-week main treatment period, study subjects will be advised to continue daily SMBG measurements and contact the clinic if the SMBG is \geq 270 mg/dL (15 mmole/L) from week 1 (week of randomization) to week 6, \geq 240 mg/dL (13.3 mmole/L) from week 6 to week 12, or \geq 200 mg/dL (11.1 mmole/L) from week 12 to week 24. During the 72-week extension period (weeks 25 to 96), subjects will continue to monitor the SMBG and contact the clinic if SMBG is \geq 200 mg/dL (11.1 mmole/L). Values of HbA1c will be evaluated in the extension period by the investigator and approved standard of oral therapy will be prescribed if HbA1c is elevated.

The investigator must review the SMBG record and FPG values in every clinic visit and assess whether any subject should receive rescue medications to treat the hyperglycemic condition during the 24-week main treatment period. The subject must be queried to assess compliance with a minimum of a 10 h fast prior to blood draw to ensure the FPG values can be accurately determined. If a subject has not fasted for 10 h, the subject must return within a week after proper fasting. The investigator will provide diet and exercise counseling and determine if the subject should receive additional rescue medication as a result of the glucose. A serum sample must be drawn prior to the rescue medication so that the last HbA1c value while the subject is on study drug only can be carried forward to 24 weeks for the primary end point analysis.

OTHER SAFETY MONITORING ACTIVITIES

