9.5.2 Secondary Efficacy Endpoints

The secondary endpoints are considered exploratory and will not be corrected for multiplicity. The first secondary hypothesis is that EGT0001442 reduces FPG at weeks 2 and 24 when compared to controls. Change in FPG for each follow up visit will be estimated as follow-up minus baseline and the two treatment groups will be compared with two paired t-tests.

The second hypothesis is that EGT0001442 reduces the HbA1c to less that 7% of more patients when compared to placebo. HbA1c categories will be assessed for each patient as <7% or \geq 7% of each subject. The 2x2 contingency table of treatment by HbA1c category will be analyzed with a χ^2 test.

The third hypothesis is that EGT0001442 reduces blood pressure compared to placebo. Systolic and Diastolic blood pressure will be measured at baseline and at weeks 2 and weeks 24. Change in each blood pressure metric for both follow up visits will be estimated as follow-up minus baseline and the two treatment groups will be compared with four paired t-tests.

The fourth hypothesis is that EGT0001442 reduces body weight compared to placebo. Body weight will be measured at baseline and at weeks 2 and weeks 24. Change in body weight for both follow up visits will be estimated as follow-up minus baseline and the two treatment groups will be compared with two paired t-tests.

The final secondary hypothesis is that EGT0001442 induced change in HbA1c is evident over time, present at week 24 and maintained over the 96 weeks of the study. HbA1c is collected at baseline and weeks 2, 6, 12, 24, 36, 48, 60, 72, 84 and 96. Repeated measures of HbA1c will be analyzed with a linear mixed effect model to assess the overall treatment effect. Subsequently the change in each time point will be estimated as described for the primary endpoint and evaluated with 10 t-tests.

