### 3.5 Sample Size Justification

Approximately 300 subjects will be enrolled and equitably allocated to receive either EGT0001442 20 mg capsules or placebo.

The sample size of 150 subjects per group was calculated based on the following assumptions:

- The mean change from baseline to Week 24 in HbA1c in the active dose group will be approximately -0.4%.
- The placebo group will not experience a substantive mean change in HbA1c from baseline to week 24.
- The standard deviation of this change is the same for both groups and is 1.0%.
- The two groups are independent, the study design is balanced, and the two-sided significance level for the hypothesis is 0.05.

Under the above assumptions, an evaluable sample size of 133 evaluable subjects per treatment arm yields approximately 90% power that EGT0001442 treatment will be found to be significantly different from placebo. A sample size of 150 subjects per treatment arm will be enrolled to account for any subject lost-to-follow-up.

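### By-visit HbA1c t-tests at Weeks 36 to 96 exclude post-rescue values although rescue follows high HbA1c, so a maintained effect is expected to look smaller if SDs are equal

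*SAP*

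**What the plan says.** Protocol 9.5.2 states a durability hypothesis for HbA1c: the effect is "present at week 24 and maintained over the 96 weeks of the study". It assesses this first with a linear mixed model on repeated HbA1c, then with t-tests at each time point. SAP 2.2 keeps the objective of describing HbA1c change out to Week 96.

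SAP 7.2.1 plans the by-visit two-sample t-tests twice, once with LOCF at all visits and once on observed cases (OC). For the second, "The OC algorithm analysis will exclude any post-rescue values". SAP 5.3.2 treats post-rescue efficacy values as missing, and SAP 5.3.1 rules out imputation after Week 24. Shell 14.2-1.2 nevertheless presents LOCF results through Weeks 96 and 97.

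On rescue in the extension, Protocol 3.1 says "approved standard of oral therapy will be prescribed if HbA1c is elevated". SAP 3.4 releases HbA1c values to investigators once all subjects have completed 24 weeks.

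SAP 7.3.1 plans, as exploratory, a mixed model on all pre-rescue HbA1c through Week 96. Its shell (14.2-1.4) lists treatment and visit as the only factors. SAP 7.3.2 adds by-visit ANCOVA under both LOCF and OC.

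**The concern.** The OC t-test at a late visit compares the subjects who have not yet been rescued. An unadjusted comparison of that kind estimates the no-rescue difference without bias only if leaving the comparison is unrelated to HbA1c. Here the therapy rule makes it depend on HbA1c. An effective drug keeps more active subjects below whatever level prompts added therapy, so the placebo group that remains is the more heavily selected toward good control, and the gap between arms narrows.

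At stake is the reading of Weeks 36 to 96. An effect that is in fact maintained could appear to fade, and the late tests would lose power to selection as well as to smaller numbers.

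**Working it through.** **Inputs from SAP 3.5.** Active arm: "The mean change from baseline to Week 24 in HbA1c in the active dose group will be approximately -0.4" percentage points. Placebo: "The placebo group will not experience a substantive mean change in HbA1c from baseline to week 24". Variability: "The standard deviation of this change is the same for both groups and is 1.0" percentage points. Alpha is 0.05 two-sided. Enrolment is 150 per arm.

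**The plan's own figure.** n = 2(1.960 + 1.282)² × 1.0² / 0.4² = 131.3, which rounds up to 132 per arm; the exact t calculation gives 133. The SAP's statement that "an evaluable sample size of 133 evaluable subjects per treatment arm yields approximately 90% power" therefore reproduces, as in effect does the protocol's 131. With all 150 per arm observed, power is 93%.

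**Mechanism, checkable by hand.** Take one visit with change distributed N(0, 1) on placebo and N(-0.4, 1) on active. Remove every value above a cut c (an assumption). The remaining mean is μ - σφ(a)/Φ(a), with a = (c - μ)/σ.

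| c | Removed, placebo / active | Mean, placebo | Mean, active | Difference |
|---|---|---|---|---|
| 0.5 | 31% / 18% | -0.509 | -0.726 | -0.217 |
| 1.0 | 16% / 8% | -0.288 | -0.563 | -0.275 |
| 1.5 | 7% / 3% | -0.139 | -0.468 | -0.329 |

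The true difference is -0.40 in every row. At c = 1.0 with the active SD raised to 1.2, the active mean is -0.4 - 1.2 × 0.2020/0.8783 = -0.676 and the difference -0.388. At SD 1.3 it is -0.450. Direction therefore depends on the SD ratio.

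**Longitudinal simulation.** SAP inputs: effect -0.4, held constant to Week 96; SD of change 1.0 in both arms. Assumptions not in the documents: baseline HbA1c N(8.2, 0.8) restricted to 7 to 10; serially correlated visits; rescue when HbA1c exceeds a threshold of 7.5 to 9.5 from Week 24 (10 before), with probability 0.5 or 1; no other dropout. The thresholds are devices for the calculation, not proposals.

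Week 96 differences (truth -0.40):

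- OC t-test: -0.20 to -0.32. Attenuation is 1 - 0.32/0.40 = 20% to 1 - 0.20/0.40 = 50%.
- Likelihood repeated measures with separate arm-by-visit means, same pre-rescue data: -0.38 to -0.41.
- LOCF: -0.36 to -0.42.

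Power at Week 96, 150 randomised per arm, certain rescue:

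| Threshold | Mean n left, placebo / active | OC t-test | Same n, no selection |
|---|---|---|---|
| 8.0 | 35 / 53 | 22% | 43% |
| 8.5 | 58 / 78 | 39% | 63% |
| 9.0 | 84 / 103 | 58% | 77% |
| No rescue | 150 / 150 | 92% | 92% |

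The last two columns separate the cost of selection from the cost of fewer subjects.

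**Sensitivity.** Attenuation persisted for baseline means 7.8 to 8.6, serial correlation 0.3 to 0.9, and regression to the mean. With no effect at any time, OC showed -0.01 to 0.00. With active SD 1.15 times placebo, OC gave -0.37 to -0.39; at 1.2 times, -0.43 to -0.44; at 1.3 times, -0.51 to -0.53.

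**Do the other analyses cover it?** When the true effect fades to 0 by Week 96, LOCF still shows -0.11 to -0.20, because it carries earlier values forward. In a separate simulation with a constant -0.40 and equal SDs, OC ANCOVA gave -0.17 to -0.31, no better than the OC t-test (-0.22 to -0.33), while likelihood gave -0.36 to -0.40. A mixed model with only treatment and visit forces one treatment difference across all visits, so the Week 96 difference in shell 14.2-1.4 would be a pooled effect.

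**The case against.** Several points on the other side stand.

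- A reader might infer that the OC t-test is the only by-visit comparison after Week 24. That follows from SAP 5.3.1 alone, but SAP 7.2.1 and shell 14.2-1.2 also plan LOCF at all visits, and 5.3.1 itself refers to Section 7 for which analyses use LOCF. The documents conflict and do not settle the matter.
- A reader might infer that rescued subjects are removed altogether. Only their post-rescue values are; earlier visits stay.
- The better method is largely planned already, in SAP 7.3.1. The gap is its status and its listed terms.
- These endpoints are secondary or exploratory, with uncorrected nominal p-values (Protocol 9.1.2, SAP 5.2). No formal decision turns on them. Attenuation would leave durability looking unsupported; it would not amount to rejecting a true hypothesis, and it is no false-positive risk when there is never an effect.
- Rescue is tabulated by arm and time, and summaries including post-rescue values are planned, so unequal rescue would be visible.
- Likelihood estimation is close to unbiased in the simulation partly by construction, because simulated rescue depends on recorded HbA1c. In the main period rescue follows SMBG, FPG and investigator judgement while HbA1c is blinded, so missing at random given HbA1c history is plausible but not guaranteed. Protocol 3.1 helps by requiring a sample before rescue.

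These points narrow the concern. They do not make the OC t-test a sound basis for a durability statement: visible imbalance is not adjustment, and none of the companion analyses, as written, gives a Week 96 contrast free of the same or another bias.

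**Conclusion.** The concern holds for HbA1c at Weeks 36 to 96. If the drug works and the SDs are equal, a maintained effect is expected to look about 20% to 50% smaller at Week 96 in the OC t-tests. That range rests on assumed rescue thresholds, since the documents give neither an HbA1c threshold nor a rescue rate.

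A reader might infer that the bias is always toward no difference. The documents do not support that: it is absent if there is never an effect, small at an SD ratio near 1.15, and reversed near 1.2. Nor should the figures be carried over to FPG, weight or blood pressure. Those were not quantified, the durability hypothesis concerns HbA1c only, and weight and blood pressure do not trigger rescue.

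The available protocol is the February 2011 original, whereas the SAP's shells cite later versions, so the durability wording should be checked against the protocol version in force. The conflict between SAP 5.3.1 and 7.2.1 is internal to the SAP and stands regardless. The change is worth making before unblinding, but it does not affect the Week 24 primary analysis.

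**What to change.** 1. Reconcile SAP 5.3.1 with 7.2.1 and shell 14.2-1.2 on whether LOCF is used after Week 24.
2. For HbA1c, name the repeated-measures model in SAP 7.3.1, on all pre-rescue observations, as the durability analysis. Specify categorical visit, treatment-by-visit and baseline HbA1c, and amend shell 14.2-1.4 to match.
3. Take the Weeks 36 to 96 differences, confidence intervals and nominal p-values from that model.
4. Keep the protocol's by-visit OC t-tests as supportive or descriptive, with a footnote that exclusion depends on the outcome.

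The cost is minor SAP and shell edits. No new data are needed, the procedure is already planned, and the mixed model is the method Protocol 9.5.2 names first. The price is reliance on missing at random given recorded HbA1c, which the SAP should state.

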### 7.2.2 FPG Change from Baseline over Time

The continuous secondary efficacy endpoints of FPG change from baseline at Week 2 and Week 24 and FPG change from baseline by visit will be analyzed analogous to the primary endpoint using a 2 sample t-test. One analysis will be performed using the LOCF algorithm for all visits, and a separate analysis will be performed using OC algorithm. The OC algorithm analysis will exclude any post-rescue values.

The pattern of FPG over time and change from baseline over time will be evaluated both descriptively using summary statistics and graphically at each scheduled visit during the entire duration of the study, excluding post-rescue measurements. Descriptive summaries will also be provided including post-rescue measurements.

The analyses will be performed on the full analysis set and all data will be listed.

#### 7.2.3 Body Weight Change from Baseline over Time

The continuous secondary efficacy endpoint of body weight change from baseline at Week 2 and Week 24 and body weight change from baseline by visit will be analyzed analogous to the primary endpoint using a 2 sample t-test. One analysis will be performed using the LOCF algorithm for all visits, and a separate analysis will be performed using OC algorithm. The OC algorithm analysis will exclude any post-rescue values.

The pattern of weight over time and change from baseline over time will be evaluated both descriptively using summary statistics and graphically at each scheduled visit during the entire duration of the study, excluding post-rescue measurements. Descriptive summaries will also be provided including post-rescue measurements.

The analysis will be performed on the full analysis set and all data will be listed.

### 7.2.4 Blood Pressure Change from Baseline over Time

The continuous secondary efficacy endpoints of blood pressure (both systolic and diastolic) change from baseline at Week 2 and Week 24 and blood pressure change from baseline by visit will be analyzed analogous to the primary endpoint using a 2 sample t-test. Multiple

Final – 22November2011 CONFIDENTIAL Page 22 of 30

measurements made on the same day will be averaged to measure blood pressure on that day. One analysis will be performed using the LOCF algorithm for all visits, and a separate analysis will be performed using OC algorithm. The OC algorithm analysis will exclude any post-rescue values

The pattern of blood pressure over time and change from baseline over time will be evaluated both descriptively using summary statistics and graphically at each scheduled visit during the entire duration of the study, excluding post-rescue measurements. Descriptive summaries will also be provided including post-rescue measurements.

The analysis will be performed on the full analysis set and all data will be listed.

### 7.2.5 Proportion of Subjects who Achieved HbA1c < 7% Response Levels

The categorical secondary efficacy endpoint of the proportion of subjects achieving HbA1c < 7% response level by visit will be analyzed by treatment comparisons that utilize a chi-square test. One analysis will be performed using the LOCF algorithm for all visits, and a separate analysis will be performed by visit using the OC algorithm. The OC algorithm analysis will exclude any post-rescue values.

The pattern of the response data over time will be evaluated descriptively using summary statistics at each scheduled visit during the entire duration of the study, excluding post-rescue measurements. Descriptive summaries will also be provided including post-rescue measurements.

The analysis will be performed on the full analysis set and all data will be listed.

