### 3.4 Blinding, Randomization, and Bias

Eligible subjects who complete the  $14 \pm 3$  day run-in period and meet all study inclusion/exclusion requirements will be randomized in a 1:1 ratio to receive EGT0001442 20 mg/day or placebo according to a computer-generated randomization schedule. Subjects will be assigned to treatment groups in sequential order as they qualify for the study, using a centrally located and managed interactive web response system (IWRS). Randomization will be stratified by study center and screening HbA1c ( $\geq 7$  to < 8.5% or  $\geq 8.5$  to 10%). The study will be conducted at multiple investigative sites and will likely involve variable numbers of subjects at each site. Enrollment will be on a competitive basis but each site will be capped at 15% of the total randomized subjects (45 subjects).

The study drug will be blinded to the sponsor, investigators, study coordinators, pharmacists, study subjects, and the cardiovascular adjudication committee members. Upon randomization, each subject will receive a subject randomization number and drug kit(s) assigned to the subject. To maintain blinding of the treatment, the values of the HbA1c after dosing starts will remain blinded to all study personnel and subjects until all subjects have completed the 24 week treatment period. After all subjects have completed the 24 week treatment period, all previous and subsequent HbA1c values will be made available to the sponsor, investigators, study coordinators, pharmacists, and the study subjects for close monitoring of subjects' safety including assessment of providing rescue medication. Subjects' treatment assignment will continue to be held from all study personnel so the remainder of the study can be conducted in a blinded fashion.

If knowledge of the test substance is needed to manage the subject's condition, the investigator will contact the IWRS to obtain the treatment assignment. If unblinding occurs for any reason, the time and reason for unblinding will be recorded on the case report form (CRF) and the sponsor must be notified within 24 hours.

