#### 5.3.1 Last Observation Carried Forward

Imputation for missing observations will be applied to selected efficacy endpoints by using the last observation carried forward method. For subjects who withdraw from the study, the last valid observation recorded on treatment (scheduled or unscheduled) will be carried forward to all remaining visits. Also, for subjects in efficacy analyses who had missing observations prior to their last observation on treatment, the closest previous non-missing on-treatment observation will be carried forward to missing visits. If a subject had missing observation(s) immediately after baseline, the baseline observation will not be carried forward and the visit(s) will be left as missing.

In general, the LOCF method will be used for all efficacy endpoints that are evaluated at or before Week 24. Beyond Week 24, all analyses will not impute any missing data; this non-imputation method will be referred to as the observed case (OC). The descriptive summaries of endpoints by study medication group will include the count of missing values at each visit. The detail of which analysis utilizes LOCF algorithm is available in Section 7.

It is expected that 24 weeks of treatment is required to obtain the full treatment effect; shorter treatment periods may result in the observation of only a partial (smaller) treatment effect. Therefore, assuming that subject discontinuation of study drug or early termination from study will occur equally and at random in both treatment groups and in each stratum, this LOCF imputation approach is expected to provide a statistically conservative estimate for the treatment effect.

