Note: This analysis uses observed values excluding those obtained after hyperglycemia rescue; no missing data imputation is performed. \* indicates statistical significance at 0.05 level.

- [1] Number of subjects with a value at baseline and at the specified visit.
- [2] The p-value is from a chi-square test for the difference in proportions.

Source Data: Listing 16.2-7.1

Programming Note: present for Weeks 2, 6, 12, 18, 24, 36, 48, 60, 72, 84, 96, 97 and 1 week follow-up.

Protocol: THR-1442-C-418 Page x of y

Table 14.2-6.3

Summary Statistics for Proportion of Subjects Achieving HbAlc <7% by Visit

(Full Analysis Set- OC)

	EGT0001442 (N=xxx)	Placebo (N=xxx)
Gcreening	xxx (xx.x%)	xxx (xx.x%)
Jeek 0	xxx (xx.x%)	xxx (xx.x%)
Jeek 2	xxx (xx.x%)	xxx (xx.x%)
Jeek 6	xxx (xx.x%)	xxx (xx.x%)
Jeek 12	xxx (xx.x%)	xxx (xx.x%)

Note: This analysis uses all observed values; no missing data imputation is performed. Source Data: Listing 16.2-7.1

Programming Note: present for Screening, Weeks 0, 2, 6, 12, 18, 24, 36, 48, 60, 72, 84, 96, 97 and 1 week follow-up.

Protocol: THR-1442-C-418 Page x of y

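### The HbA1c <7% responder endpoint is the only efficacy endpoint with no baseline-adjusted analysis, and its observed-case version drops rescued subjects from the denominator, which matters mainly after Week 24

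*SAP*

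**What the plan says.** **The test.** SAP 7.2.5 states that the proportion of subjects under 7% at each visit "will be analyzed by treatment comparisons that utilize a chi-square test". Protocol 9.5.2 plans the same: "The 2x2 contingency table of treatment by HbA1c category will be analyzed with a" chi-square test. Neither names a covariate or stratum. SAP 3.4 states: "Randomization will be stratified by study center and screening HbA1c", in two bands divided at 8.5%. SAP 7.3.2 gives supportive ANCOVA models for change in HbA1c, FPG, body weight and systolic and diastolic pressure. All contain baseline HbA1c, as a continuous value for HbA1c itself and as a category for the others. The responder endpoint has no counterpart.

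**Missing and rescued subjects.** SAP 7.2.5 plans two versions. First: "One analysis will be performed using the LOCF algorithm for all visits". The second uses observed cases: "The OC algorithm analysis will exclude any post-rescue values". A footnote repeated under shells 14.2-6.1 and 14.2-6.2 defines the subject count: "Number of subjects with a value at baseline and at the specified visit". Shell 14.2-6.2 adds that nothing is imputed. SAP 5.3.1 gives the general rule: "In general, the LOCF method will be used for all efficacy endpoints that are evaluated at or before Week 24". It then says: "Beyond Week 24, all analyses will not impute any missing data". Yet 7.2.5 and shell 14.2-6.1, whose visits run to Week 97, apply LOCF past that point.

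**Reporting.** SAP 5.2 promises confidence intervals alongside nominal p-values for secondary analyses. Shells 14.2-6.1 and 14.2-6.2 show only a p-value.

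**The concern.** A fixed 7% cut makes the starting value matter. A subject who starts just above 7% and one who starts near 10% have very different chances of crossing it. Baseline HbA1c is therefore a strong predictor of response, and the trial stratifies on its screening value. Leaving it out of every responder analysis gives away some precision on a named secondary objective.

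The OC version raises a different problem, which is selection on the outcome. A subject rescued for hyperglycaemia leaves the denominator instead of counting as not at target on study drug alone. The link is tightest after Week 24. Protocol 3.1 has therapy added in the extension when HbA1c is elevated, and SAP 3.4 releases HbA1c values at that stage partly so that rescue can be assessed. Failing the endpoint can then remove the subject from the endpoint. At stake are the size and interpretation of the responder difference through Week 96, not the primary result.

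**Working it through.** **1. The plan's own figure.** The documents give no power, response rate or rescue rate for this endpoint. The only planning figure is for the primary endpoint (SAP 3.5: difference 0.4, SD 1.0, two-sided 0.05, 90% power).

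n per arm = 2 × (1.960 + 1.282)² × (1.0/0.4)² = 131.4, so 132. The noncentral t gives 90.2% at 133 (SAP) and 89.7% at 131 (Protocol 9.2). Both stated figures are acceptable, so the same effect and SD are used below.

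**2. Value of adjusting for baseline.** Simulation, 1,500 trials per scenario, difference 0.4, SD of change 1.0. These inputs are assumptions that the documents do not give: baseline HbA1c normal, truncated to 7-10; slope of change on baseline 0, -0.3 or -0.5. CMH uses the 8.5% cut; logistic regression uses continuous baseline HbA1c. Selected results at 150 per arm (power, %):

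| Baseline mean, SD | Slope | Response, placebo / active (%) | Chi-square | CMH | Logistic | Logistic gain |
|---|---|---|---|---|---|---|
| 8.0, 0.8 | 0 | 16.9 / 26.6 | 52.5 | 55.3 | 59.9 | 7.4 |
| 8.0, 0.8 | -0.3 | 14.4 / 24.4 | 60.4 | 61.9 | 64.5 | 4.1 |
| 8.0, 0.8 | -0.5 | 12.6 / 22.7 | 64.3 | 64.8 | 65.9 | 1.6 |
| 7.8, 0.6 | 0 | 21.1 / 32.7 | 62.5 | 62.9 | 66.6 | 4.1 |
| 7.8, 0.6 | -0.5 | 18.2 / 30.6 | 71.4 | 71.2 | 72.4 | 1.0 |
| 8.3, 0.9 | 0 | 13.2 / 21.8 | 50.3 | 53.4 | 57.6 | 7.3 |
| 8.3, 0.9 | -0.5 | 8.5 / 16.5 | 56.1 | 56.9 | 57.9 | 1.8 |

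At 133 per arm the logistic gain is 1.3 to 6.4 points. Over all 18 scenarios, CMH gains between -0.3 and 3.3 points. The top of the logistic range needs change to be independent of baseline.

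**3. Type I error.** With no effect (3,000 trials, baseline 8.0, 0.8, slope -0.3), rejection was 5.5% for chi-square, 5.5% for CMH, 5.9% for logistic and 5.4% for chi-square on OC data. The Monte Carlo SE is √(0.05 × 0.95/3000) = 0.4 points. The logistic figure is about two SEs high, but a second run of 1,000 trials gave 5.9% for chi-square and 5.1% for logistic. There is no consistent difference.

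**4. The OC denominator.** Let p be the response rate with rescued subjects counted as non-responders, and r the rescue rate. If no rescued subject is a responder, the OC rate is p/(1 - r). At rescue of 15% and 5% the factors are 1/0.85 = 1.18 and 1/0.95 = 1.05.

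Examples at 150 per arm, with assumed rates. OC arm sizes are 150(1 - r). Power is by the normal approximation for two proportions.

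| Response, placebo / active | Rescue, placebo / active | OC response | Difference (points) | Power |
|---|---|---|---|---|
| 15% / 30% | 5% / 2% | 15.8% / 30.6% | 15.0 to 14.8 | 88% to 85% |
| 20% / 35% | 15% / 5% | 23.5% / 36.8% | 15.0 to 13.3 | 83% to 66% |
| 30% / 45% | 20% / 5% | 37.5% / 47.4% | 15.0 to 9.9 | 77% to 36% |

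In the step 2 simulations, with Week 24 HbA1c above 9.5% as a proxy for rescue (placebo 5.6-18.2%, active 2.3-11.0%), OC deletion cost 5.7 to 12.5 power points.

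**5. Where this applies.** Up to Week 24, LOCF keeps rescued subjects in with the HbA1c recorded at rescue (SAP 7.1, 5.3.2; shell 14.2-6.1), so step 4 does not touch that result. After Week 24, 5.3.1 permits only OC, while 7.2.5 permits both.

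**The case against.** The strongest reply is that nothing here is invalid and little depends on it. Secondary endpoints are exploratory in Protocol 9.1.2 and 9.5.2, p-values are nominal, and the sample size rests on mean HbA1c change. The main test for every endpoint is unadjusted, so a chi-square is consistent with the plan; the ANCOVA models are supportive only. All of that stands. It limits the priority but does not explain why this endpoint alone lacks a supportive adjusted analysis.

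A second reply is that 7.2.5 already plans LOCF beside OC, plus descriptive summaries that include post-rescue values. At Week 24 this is a full answer. Later it is only partial: the summaries show values under added therapy, and 5.3.1 rules LOCF out. One can argue that 5.3.1 defers to Section 7 for detail, but its statement about all analyses beyond Week 24 remains in direct conflict.

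A reader might infer three stronger things, none of them supported:
- That ignoring the stratum invalidates the chi-square. Simulated type I error is about 5%.
- That the Week 24 responder result is distorted by rescue. The LOCF version retains rescued subjects.
- That OC deletion risks a false claim of benefit. If placebo has more rescue, as one would expect, the examples show it working against the drug. The documents give no rescue rates, so that direction is itself an assumption.

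**Conclusion.** The point holds at modest severity and has two parts.

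- **Adjustment.** The responder endpoint is the only efficacy endpoint without a baseline-adjusted analysis. Adding one is worth roughly 1 to 7 power points, depending on the baseline spread and on how far change depends on baseline, with no evident type I error cost. CMH on the two strata recovers less, about 0 to 3 points.
- **OC denominator.** Deleting rescued subjects multiplies each arm's rate by about 1/(1 - rescue rate). The cost runs from about 3 power points at 5% against 2% rescue to about 40 at 20% against 5%. It is confined to OC and matters most at Weeks 36-96.

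The second part assumes that rescued subjects are non-responders, that therapy added in the extension is recorded as rescue, and that the percentage base in shell 14.2-6.2 is subjects with a value at the visit. The shell's footnotes imply the last of these without stating it.

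**What to change.** 1. For the Week 24 LOCF responder endpoint, add a logistic regression on treatment and continuous baseline HbA1c, with or without the screening stratum. Report the adjusted odds ratio and a risk difference with 95% CI, and add the interval to the responder shells as SAP 5.2 requires. Keep the protocol's chi-square alongside.
2. In the OC responder analyses, especially Weeks 36-96, keep subjects rescued before the visit in the denominator as non-responders, and state the denominator in shell 14.2-6.2.
3. Reconcile SAP 5.3.1 with 7.2.5 and shell 14.2-6.1 on LOCF after Week 24.
4. Do not extend the non-responder rule to all discontinued subjects in the main analysis. That changes the estimand and should be at most a sensitivity analysis.

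The cost is SAP wording, one model and small shell edits on data already collected, settled before the Week 24 unblinding and recorded in SAP Section 10. Because the chi-square stays, the Protocol's test is still carried out. The one drawback is that the odds ratio is conditional on baseline, which is why the risk difference is shown beside it.
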